**Table 3: Comprehensive Acne Severity Scale (CASS)**

GRADE*		DESCRIPTION
Clear	0	No lesions to barely noticeable ones. Very few scattered comedones and papules.
Almost clear	1	Hardly visible from 2.5 metre away. A few scattered comedones, few small papules and very few pustules.
Mild	2	Easily recognisable; less than half of the affected area is involved. Many comedones, papules and pustules.
Moderate	3	More than half of the affected area is involved. Numerous comedones, papules and pustules.
Severe	4	Entire area is involved. Covered with comedones, numerous pustules and papules, a few nodules and cyst.
Very severe	5	Highly inflammatory acne covering the affected area, with nodules and cyst present.

Inspection is done at a distance of 2.5 meters away for acne on face, chest and back.

▪ **Chest area defined as:**

Anterior torso superiorly defined by suprasternal notch extending laterally to shoulders and inferiorly by a horizontal line defined by the xiphoid process.

▪ **Back area defined as:**

(Is demarcated by the) superior aspects of the shoulders extending to the neck and inferiorly by the costal margins.

- The participants will be treated with once weekly isotretinoin at a dosage of 1-1.5mg/kg/week. Exact dosage will be determined by the provider.
- Efficacy will be determined by having one trained individual (“Photo Reviewer”) grade patients’ facial photographs to limit interrater reliability bias. This person will not be told what is being used as the study drug, and will not be told any details of the study, including that all participants are on the study drug, in order to limit observer bias (blinded). Every month, clinical photos will be submitted for each patient enrolled in the study. The participants will have these photos taken at monthly follow-up visits (monthly follow-up visits are standard of care per requirements of IPLEDGE, the medication monitoring system for isotretinoin). For in-person visits, these monthly photos will be taken by the provider or staff in clinic and directly uploaded to the Epic electronic medical record. For any virtual clinic visits (given the COVID-19 pandemic), the monthly photos will be submitted into MyChart by the patient.

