- The Study Coordinator (Dermatology research fellow), who per the study consent form has permission to access participants’ medical records for the purpose of the study, will follow each patient through Epic electronic medical record to confirm that photos are submitted in a timely manner.
- A separately trained individual (“Data Retriever”), who per the study consent form has permission to access participants’ medical records for the purpose of the study, will submit any uploaded photos (baseline and at the end of each

month) from Epic to the Photo Reviewer by secure, encrypted email, labeling only with participant number and date of photo. This ensures that the Photo Reviewer is always reviewing only individual photos and will not ever enter the patient's medical chart to further limit bias.

- Photo Reviewer will receive photos and document a monthly CASS grade for each participant (in encrypted Excel only accessible by study team members, using study participant numbers without patient identifiers, **attachment F**). Baseline photos will all be a grade 3 (moderate) based on study inclusion criteria. "Improvement" is defined as decrease in grade from a 3 (moderate) to either a 2 (mild), 1 (almost clear), or 0 (clear). "Failure" is defined as showing no improvement (remaining a grade 3), increasing grade of 4 (severe) or 5 (very severe), or requiring additional oral treatment (for example, worsening acne requiring conventional dose isotretinoin). Treatment success can then be calculated as the percentage of participants with improvement out of the total number of participants at the end of four months, in addition to treatment success after each month of treatment.
- Any participants who take any oral tetracycline antibiotics or trimethoprim-sulfamethoxazole during the study period (for a reason besides acne) will be removed from the study in order to prevent any confounding. Patients requiring these medications for acne after the study period has begun will remain included in the study and will be listed as intervention "failure" as above. Participants will be allowed to continue use of topical acne cleansers and treatments during the study as per standard of care.

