### **14.0 Withdrawal of Subjects (if applicable)**

- Study investigators may withdraw a participant from the study at any time at their discretion. Circumstances can include when a participant's safety may be compromised such as when a participant is experiencing adverse events requiring discontinuation of the drug, if the study is stopped in relation to risk to participants, or when the participant is non-compliant with the medication regimen.
- A study investigator will inform the participant that he or she has been withdrawn from participation and the reasons therefore.

- At any time, a participant can withdraw from participation in some or all components of the study.
  - When the participant withdraws, the participant will no longer receive isotretinoin at the experimental regimen.
  - The participant's medical record or other confidential records will not be accessed by the investigator.
  - The data collected to the point of withdrawal will remain part of the study records.
- At a minimum, documentation of the participant's withdrawal will include the date, rationale, and which component the participant is withdrawing.
- The Primary Investigator will inform the IRB of the number of participants who withdrew and the reason for withdrawal.

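### The month-four success rate can be read as a rate among those still in the study, and participants without a month-four grade carry no outcome

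*Protocol*

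**What the plan says.** Section 10.0 fixes the efficacy calculation. Improvement is a fall in CASS grade from 3 to 2, 1 or 0. Failure is a grade that stays at 3, a grade of 4 or 5, "or requiring additional oral treatment". Success is the percentage improved "out of the total number of participants at the end of four months, in addition to treatment success after each month of treatment".

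The grade comes from photographs: "Every month, clinical photos will be submitted for each patient enrolled in the study". Clinic staff take them at in-person visits. At virtual visits "the monthly photos will be submitted into MyChart by the patient". The coordinator checks that they arrive.

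There are several ways to have no month-four grade:

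- **Withdrawal by the participant.** Section 14.0 says that "a participant can withdraw from participation in some or all components of the study", and that after this the participant's "medical record or other confidential records will not be accessed by the investigator".
- **Withdrawal by the investigator.** Section 14.0 also says "Study investigators may withdraw a participant from the study at any time at their discretion", with adverse events and non-compliance among the examples. Data collected so far are kept after a participant withdraws, but no month-four outcome is assigned on either route.
- **Non-acne antibiotics.** Under Section 10.0, participants who take the listed antibiotics for another reason "will be removed from the study in order to prevent any confounding". Those who need them for acne stay in and count as failures.
- **A missing photo.** No rule is given.

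Section 6.0 sets the target at 50 with attrition in mind. Section 12.0 says that no statistical analysis will be done and observations will be reported.

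**The concern.** This rate is the only efficacy figure that the protocol defines, and Section 16.0 makes larger randomized studies depend on participants showing benefit. If the denominator is whoever is left at month four, people who stop for adverse events or non-compliance vanish from the result. Those are reasons to leave that may well be related to outcome. If the denominator is everyone, the rate already treats ungraded people as not improved, but nothing says so, and the improved and failed percentages will not add up to 100%. Two readers who follow the text could report different primary results from the same data. The month-by-month rates share the problem.

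**Working it through.** The protocol states no expected success rate, loss rate or precision, so it has no figure of its own to reproduce. The enrollment numbers 50 and 30 come from Section 6.0. The loss and response rates below are assumptions.

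**Formulas.** Let N be the number who start, m the number graded at month four and x the number improved. The remaining-participants reading gives x/m. The all-participants reading gives x/N, with ungraded people implicitly not successful. Intervals are exact (Clopper-Pearson) 95%.

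**The two readings, about 80% of those graded improved**

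| N | Loss | x/m | x/N | Gap |
|---|---|---|---|---|
| 50 | 0 | 40/50 = 80.0% (66.3 to 90.0) | the same | 0 |
| 50 | 5 (10%) | 36/45 = 80.0% (65.4 to 90.4) | 36/50 = 72.0% (57.5 to 83.8) | 8.0 points |
| 50 | 10 (20%) | 32/40 = 80.0% (64.4 to 90.9) | 32/50 = 64.0% (49.2 to 77.1) | 16.0 points |
| 30 | 6 (20%) | 19/24 = 79.2% (57.8 to 92.9) | 19/30 = 63.3% (43.9 to 80.1) | 15.9 points |

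**Labels.** In the 50-starter, 20% loss case, 32/50 = 64% are improved, 8/50 = 16% failed and 10/50 = 20% are neither.

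**Direction.** In the same case, suppose the 10 lost had improved at some other rate. The rate among all 50 would then be:

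- at 40%: (32 + 4)/50 = 72.0%, so the graded-only 80% is too high
- at 80%: (32 + 8)/50 = 80.0%, so there is no bias
- at 100%: (32 + 10)/50 = 84.0%, so the graded-only rate is too low

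**Monthly rates.** As an extreme case, let 32 be improved every month, let every loss be a non-improver, and let 50, 46, 43 and 40 be graded. The rates are 32/50 = 64.0%, 32/46 = 69.6%, 32/43 = 74.4% and 32/40 = 80.0%. The rise of 16 points comes from loss alone.

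**Non-acne antibiotics.** If 2 of the 10 losses are such removals, the rate is 32/(50 − 2) = 32/48 = 66.7% without them and 32/50 = 64.0% with them counted as not successful.

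**The case against.** The strongest reply is that the sentence is not really ambiguous. Its two time phrases run in parallel, so both may simply say when the rate is calculated, leaving all participants as the denominator. On that reading ungraded people already count as not successful, because only improvement enters the formula, and the missing label does not distort the rate. This is a fair reading, perhaps the more natural one. It does not exclude the other, and nothing elsewhere in the protocol settles the matter. So a reader may not infer that the protocol commits to a completers-only rate.

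Four other inferences are tempting and not supported:

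- **That success is certainly overstated.** The protocol gives no reason to assume that those who leave do worse by any given amount. Part of the lack-of-benefit route is already covered, since additional oral treatment is a failure. Staff photos and coordinator checks should keep missed photos few.
- **That the protocol expects 40% attrition.** The step from 50 to 30 would fit that rate only if 30 meant completers. Section 6.0 calls it a minimum enrollment.
- **That removal for non-acne antibiotics is an oversight.** Section 10.0 gives its reason and contrasts these participants with those who remain as failures. Counting a later photo of theirs as a success would bring back the confounding that the removal is meant to avoid.
- **That many people never prescribed the drug would enter the denominator.** Section 13.0 excludes patients with significant baseline laboratory abnormalities from enrolling, and Section 10.0 speaks of participants as treated. Only someone who consents and then leaves before prescription for another reason is unclear.

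It can also be said that analysis sets belong in a separate analysis plan, and that a proof-of-concept study needs no inference. The first does not answer the point, because the protocol itself fixes the formula and both outcome definitions. On the second, a descriptive percentage still needs one denominator. The interval is a lesser addition and does not resolve the denominator.

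**Conclusion.** The point holds in a limited form. The success formula admits a reading on which withdrawn and ungraded participants leave the rate. On the other reading they are counted but unlabelled. With 50 starters and 80% of those graded improved, the choice is worth 8 points at 10% loss and 16 points at 20% loss. The 8-point gap is smaller than the sampling uncertainty: 36/45 has an interval from 65.4% to 90.4%. All sizes depend on assumed loss and response. Overstatement on the remaining-participants reading is likely, because withdrawal for adverse events or non-compliance is unlikely to be unrelated to outcome, but it disappears if those lost improve as often as those graded. The point should be fixed, because it touches the primary result and the repair is short.

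**What to change.** In Section 10.0, next to the success formula, state that:

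- the main denominator, at month four and at each month, is all participants prescribed the study drug, apart from the non-acne antibiotic removals described below
- additional oral acne treatment remains a failure, as now
- anyone without a grade at that time counts as not successful
- the rate among those graded is reported as secondary, with losses by reason and month
- participants removed for non-acne antibiotics stay removed, no later photo of theirs counts as a success, their number is reported, and a sensitivity result counts them as not successful

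In Section 12.0, keep the descriptive aim but report the month-four rate with an exact 95% confidence interval. For example, 80% carries 61% to 92% with 30 people (24/30) and 66% to 90% with 50 (40/50).

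The cost is a few sentences. Prescriptions are already recorded in Epic (Section 18.0), so the denominator needs no dosing log. No extra follow-up is needed, and clinical care does not change. The downside is a more conservative headline rate: losses unrelated to treatment also count against it, and someone prescribed the drug who never took it stays in. The secondary rate and the table of losses show how much this matters.

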### 4.0 Study Endpoints (if applicable)

Primary endpoint: efficacy

Secondary endpoints: patient satisfaction, adverse effects

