## **6.0 Number of Subjects**

Target enrollment is 50 participants to allow for attrition. Minimum expected enrollment is 30 participants.

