- Photo Reviewer will be a blinded medical student because all of the dermatology residents will be participating in the clinical care of study participants. The Photo Reviewer will be trained by the Primary Investigator (Dermatology Resident) and Study Coordinator (Dermatology Research Fellow) on how to use the objective CASS grading system.
- Data Retriever will be a Dermatology resident who will be trained by the Primary Investigator (Dermatology Resident) and Study Coordinator (Dermatology Research Fellow).
- All participants, regardless of whether they show "improvement" or "failure," will be followed for up to four months after the study period to assess for recurrence of acne. During this period, any further treatment decisions will be made by the patient and his or her clinician. Any participants who choose to continue once weekly isotretinoin will be asked to upload clinical photos and patient satisfaction surveys monthly through MyChart. Other participants who discontinue the isotretinoin will be asked about their follow-up acne treatment.

To determine patient adverse effects (secondary endpoint), we will monitor for side-effects of the interventional medication.

- Per standard of care, patients will be enrolled in IPLEDGE, requiring extensive counseling before starting the isotretinoin medication, monthly follow-up visits for males and females, and monthly urine pregnancy tests for females.
- Each patient will fill out a survey at baseline (**attachment C**) and at each monthly visit (**attachment G**) inquiring about potential side-effects of isotretinoin (with severity) including dry skin, dry mucous membranes (lips,

eyes), GI upset, bone or muscle pain, night vision abnormalities, mood swings/depression, headaches, delayed wound healing. If the follow-up visit between the patient and his or her clinician is virtual, the attached surveys will be sent in an encrypted email for completion by the participant. Photos of each completed survey will be uploaded into the patient's chart either at their clinic visit or by the patient via MyChart (virtual visit).

- Per standard of care, laboratory blood work (CBC, CMP, lipid panel) will be obtained prior to starting the medication and will be repeated two months into the study period (after two clinical follow-up visits, also per standard of care and confirmed by PRA), or more frequently if clinically indicated. The results will be reviewed from the medical record.

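### Post-study follow-up is meant to assess recurrence, but no photos are requested from participants who stop isotretinoin, so recurrence off drug gets no CASS grade

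*Protocol*

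**What the plan says.** The relevant text is in Protocol section 10.0 (Study Design / Methods), after the CASS table.

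- **Purpose of follow-up.** All participants, whether classed as improved or failed, "will be followed for up to four months after the study period to assess for recurrence of acne". Treatment in this period is left to the patient and clinician.
- **Those who continue.** "Any participants who choose to continue once weekly isotretinoin will be asked to upload clinical photos and patient satisfaction surveys monthly through MyChart".
- **Those who stop.** "Other participants who discontinue the isotretinoin will be asked about their follow-up acne treatment". No photo, CASS grade, lesion count, visit or survey is named for them.
- **How a grade arises.** "Photo Reviewer will receive photos and document a monthly CASS grade for each participant". The photos reach that reviewer from the medical record through the Data Retriever.
- **When study photos are taken.** At monthly visits, which the protocol explains by noting that "monthly follow-up visits are standard of care per requirements of IPLEDGE, the medication monitoring system for isotretinoin".
- **Background treatment.** "Participants will be allowed to continue use of topical acne cleansers and treatments during the study as per standard of care".

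Section 4.0 gives efficacy as the primary endpoint and then "Secondary endpoints: patient satisfaction, adverse effects". Recurrence is not listed there or among the objectives in section 1, and it is not defined anywhere in the protocol.

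**The concern.** The follow-up has one stated purpose, which is to see whether acne returns. The group that can show whether it returns after the drug is stopped is the group from which no photo is requested. Photos are requested from people still taking the drug, and in them the photos show response on continued treatment.

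The question put to stoppers is about treatment, not acne severity. It would pick up a new oral treatment. It would not separate a participant who remains at grade 0 to 2 on topicals from one who is back at grade 3 on the same topicals, since topicals are permitted throughout.

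Section 2.0 relies on similar recurrence rates with alternative and conventional dosing, and acknowledges an older study that found otherwise. Section 16.0 looks ahead to larger randomized studies if benefit is seen. Graded off-drug data would inform that step, and a photo not taken at the time cannot be recovered by any later analysis.

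**Working it through.** The protocol gives no recurrence rate, stopping rate or figure of its own to reproduce, so the check is mainly one of setting the instructions side by side.

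**Step 1: path to a grade (section 10.0).** Photo uploaded, forwarded by the Data Retriever, graded on CASS by the Photo Reviewer. Without a photo there is no grade.

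**Step 2: what is requested after the study period (section 10.0).**

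| | Continues weekly isotretinoin | Stops |
|---|---|---|
| Monthly photo | Yes | Not named |
| Satisfaction survey | Yes | Not named |
| Question on acne treatment | Not named | Yes |
| Photos requested over up to 4 months | Up to 4 | 0 |

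**Step 3: does another instruction fill the gap?** Section 10.0 also says that photos are submitted monthly for each enrolled patient. Those photos are tied to visits required by the isotretinoin monitoring system, and the follow-up paragraph then gives its own, different instructions. Had the general rule covered everyone after the study period, a separate photo request to continuers would have been unnecessary. The pregnancy test after stopping (sections 10.0 and 15.0) does not assess acne. No other section supplies an acne assessment for stoppers.

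**Step 4: size.** Let k be the number of participants who improved by month four and then stop.

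- Off-drug monthly grades possible per stopper: up to 4 (one per month for up to four months).
- Off-drug monthly grades provided for: 0.
- Not collected: up to 4 × k.

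The protocol does not give k. Section 6.0 sets a target of 50 and states: "Minimum expected enrollment is 30 participants". Hence:

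- Lower bound, k = 0: 4 × 0 = 0.
- Ceiling at 30 participants: 4 × 30 = 120.
- Ceiling at 50 participants: 4 × 50 = 200.

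The ceilings would require every participant to improve, stop and be followed for the full four months. They are limits, not estimates.

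**The case against.** The best defence is that the text is loose and does not actually exclude photos from stoppers. It never says that treatment is the only thing asked, the lead sentence covers all participants, and the general monthly photo rule refers to each enrolled patient. It is correct that "only" is an inference. It remains the natural reading, because the two groups are given contrasting instructions in adjacent sentences and nothing but the treatment question is named for stoppers.

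Second, the protocol does not state that continuers' follow-up photos will be graded. That is fair: what the text firmly supports is photos requested against photos not requested. Grading of continuers' photos assumes that the existing process carries on. The gap for stoppers does not depend on that assumption.

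Third, the treatment question has real value. Needing additional oral treatment is part of the protocol's own definition of failure, so the question captures that component. Study staff may also consult the chart (section 12.0). What remains missed is relapse left untreated or managed with topicals, and chart notes would not be masked CASS grades.

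Fourth, the stakes are modest. Recurrence is not an endpoint, section 12.0 plans no statistical analysis, and stoppers and continuers select themselves, so even complete photos would give descriptive data only. All of this stands and limits the weight of the point. It does not explain why a stated purpose should be left without the measurement it needs.

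**Conclusion.** The concern holds. As written, the follow-up can show response on continued treatment but cannot grade recurrence off drug on the study's own scale. The firm figure is per participant: 0 photos requested from someone who stops, against up to 4 from someone who continues. The totals of 0 to 120 and 0 to 200 are bounds only. The direction and size of any resulting bias are unknown.

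The conclusion assumes that stoppers are asked for nothing beyond what section 10.0 names; the attachments, including the data sheet and monthly survey, were not available. The month-four success percentage and the satisfaction and adverse-effect results are not touched. This should be corrected because correction is cheap and the lost data are irrecoverable, but it does not threaten the main result.

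**What to change.** 1. In section 10.0, ask every participant in follow-up, including those who stop, for the same monthly MyChart photos, and state that all follow-up photos go to the masked Photo Reviewer for CASS grading. The satisfaction surveys can be requested alongside for consistency, but they are not needed to grade recurrence.
2. Define recurrence on the CASS scale, for example as a return to grade 3 or higher among participants who had improved at month four and then stopped.
3. Report recurrence in stoppers with their reported follow-up treatment beside it. Report continuers separately, as response on continued treatment. Give the number of stoppers with and without photos at each month.

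The cost is a short wording change to the protocol, and to the consent form if it describes follow-up in the same way (the form was not available). The upload route, reader and coordinator are already in place, and no visit or treatment decision changes. The downside is up to 4 extra photos, and up to 4 surveys if these are included, per participant who stops. There would also be more masked reading, more chasing by the coordinator, and some non-response among people no longer on the drug.

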## 1. Objectives / Specific Aims

The objectives of the study are to:

- determine if once weekly dosed isotretinoin is effective for moderate acne vulgaris
- evaluate patient satisfaction with once weekly dosed isotretinoin for moderate acne vulgaris treatment
- identify any adverse effects associated with once weekly dosed isotretinoin for moderate acne vulgaris treatment

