## **8.0 Recruitment Methods**

- Recruitment will occur during standard of care visits to the Dermatology Clinics including its virtual visits.
- The first person to inform eligible patients about the study will be a clinician directly involved in the eligible patient's care. The clinician will first determine if the patient may meet criteria (score of 3, moderate acne, on CASS clinical scale as described in more detail in section 10.0). If the patient expresses interest in the study, the clinician or study co-investigators will approach the patient without coercion and with the emphasis on the voluntary aspect of being enrolled in this study. He/she will also be told in a caring manner that no matter his/her decision, it will not affect his/her care. This discussion will take place either in-person during the patient's clinic appointment or over telephone within one business day of the appointment.
- If the discussion takes place in-person during the clinic appointment, the patient will be provided a printed recruitment pamphlet reiterating the information regarding the study (**attachment A**). Eligible patients who agree to participate will sign the study consent form. Weight will be obtained. A baseline photograph will be taken and uploaded into the patient's medical chart (Epic). Two baseline surveys (Dermatology Life Quality Index survey to assess patient satisfaction and a second survey regarding potential isotretinoin adverse effects) will be completed by the patient (**attachments B and C, respectively**). The patient's clinician will then counsel the patient on isotretinoin and IPLEDGE and enroll the patient in the IPLEDGE system following all prompts. The clinician will order baseline laboratory blood work (all patients) and

urinary pregnancy test (females). Once blood work has returned and is without any clinically significant abnormalities (see section 13.0), the weekly isotretinoin (at dose 1-1.5 mg/kg per week) will be prescribed by the clinician (for males). Females will need to wait an additional month to have a second negative pregnancy test before starting the medication per IPLEDGE standard of care. After a second negative pregnancy test at next monthly visit, the clinician can prescribe the weekly dosed isotretinoin.

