- Pregnancy test data will be collected from the medical record as these will be performed as part of the clinical care of the patient. Female participant's individual providers will order pregnancy tests, which per standard of care are typically collected at baseline x 2 (one month apart), every month while on the medication, and at least one month after stopping the medication. If patients have any significant laboratory abnormalities that could be related to the medication, the medication will be discontinued.
- The Study Coordinator (Dermatology research fellow) will follow each patient through Epic electronic medical record to confirm that laboratory work and surveys are completed in a timely manner.
- Data Retriever will follow each participant's laboratory blood work and any abnormalities will be entered into the encrypted Excel sheet; this individual will also enter all survey responses into the same encrypted Excel sheet (attachment F).

To determine patient satisfaction (secondary endpoint), the Dermatology Life Quality Index (<https://www.cardiff.ac.uk/medicine/resources/quality-of-life-questionnaires/dermatology-life-quality-index>) will be administered at baseline before receiving any medication and at each monthly follow-up visit. The DLQI is the most frequently used validated, patient-reported outcome measure in dermatology trials (attachment B). License for use of survey has been obtained (attachment H).

- Data Retriever will follow each participant's surveys and enter information into the same encrypted Excel sheet as noted above.

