## 12.0 Data Management

- Participant clinical photos, signed consent form, and photos or scans of their completed surveys will be uploaded into the Media tab of Epic electronic health record either in clinic or by the patient through MyChart. Laboratory result information will result in the patient's Epic medical chart. This will keep this information secure and protected. Study team members will have permission to access study participants' medical records for the purpose of retrieving information for the study, as listed in the study consent form.
- Data Retriever will securely email ("send secure") the participant photos (deidentified) to the Photo Reviewer to score. This will occur over MUSC email only.
- Storing of synthesized study information (participant follow-up dates, scoring of clinical photos, list of any participant lab abnormalities, participant survey answers) will be entered in an encrypted Excel sheet, labeled only with participant number and without patient identifiers (**attachment F**). Only investigators directly involved with the study will have access to this encrypted Excel sheet.
- Paper consent forms will be stored in a locked office (Rutledge Tower, dermatology office floor 10). Electronic consent forms will be stored on a MUSC desktop computer that is secured by username and password. Photos of all consent forms will be taken for upload into patient's Media tab in their medical chart.
- Since this is a proof-of-concept study, there will not be any statistical analysis. Observations will be reported.
- Data will not leave MUSC.

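### Satisfaction with weekly isotretinoin is an objective and a secondary endpoint, but the only measure the protocol text names for it is a quality-of-life index, which is at best an indirect proxy

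*Protocol*

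**What the plan says.** Section 1 of the protocol sets three objectives. The second is to "evaluate patient satisfaction with once weekly dosed isotretinoin for moderate acne vulgaris treatment". Section 4.0 carries it forward: "Secondary endpoints: patient satisfaction, adverse effects". The last paragraph of text in section 2.0 also names satisfaction as a secondary endpoint.

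The instrument appears in two sections. Section 8.0, for both the in-person and the virtual route of entry, refers to the "Dermatology Life Quality Index survey to assess patient satisfaction". Section 10.0 opens its account of this endpoint with "To determine patient satisfaction (secondary endpoint), the Dermatology Life Quality Index", and says that the index "will be administered at baseline before receiving any medication and at each monthly follow-up visit".

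The other patient survey is attachment C at baseline and attachment G monthly. Section 10.0 describes it as "inquiring about potential side-effects of isotretinoin (with severity) including dry skin, dry mucous membranes (lips" and other effects. For the period after the study, section 10.0 says that participants who stay on the weekly drug "will be asked to upload clinical photos and patient satisfaction surveys monthly through MyChart", without saying which form is meant. Section 12.0 adds that "there will not be any statistical analysis. Observations will be reported".

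**The concern.** Satisfaction with a treatment is the patient's judgement of that treatment: its result, burden, side-effects and cost. Skin-related quality of life is how far the skin condition interferes with daily life. The two are related, but one can move without the other. A patient's skin and life quality may improve while the patient dislikes the dryness, the monthly visits and tests, or paying for the drug. Conversely, a patient may like taking one dose a week although life quality has changed little. Participants may also continue topical treatment (section 10.0) and there is no control group, so the index can change for reasons unrelated to the weekly drug.

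What is at stake is the conclusion on one objective. Section 2.0 cites earlier work in which satisfaction was greatest under alternative dosing. If index scores are reported here under the same label, readers will set them beside those results as if patients had been asked about the regimen. An analysis plan could not repair this later, because it cannot supply answers that were never collected.

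**Working it through.** No figure is in dispute and no formula applies. The check is to set every mention of satisfaction, the index and the patient surveys side by side.

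1. **What is to be learned.** Section 1: satisfaction with the once weekly regimen. Sections 2.0 and 4.0: satisfaction as a secondary endpoint, with no measure attached.
2. **What is named as the measure.** Sections 8.0 and 10.0: the Dermatology Life Quality Index. No other satisfaction instrument is named anywhere in the protocol.
3. **What that instrument measures.** Its title says life quality, and the web address given in section 10.0 lies under quality-of-life questionnaires. Section 10.0 calls it a validated patient-reported measure. It does not say that it is validated for satisfaction with a treatment.
4. **What the scores can express.** The index is given before any drug and then monthly. The baseline value cannot be satisfaction with a drug not yet taken. The change from that value is therefore a change in skin-related quality of life. It bears on satisfaction only indirectly, and no rule in the protocol turns a score or a change into a statement about satisfaction.
5. **Whether another source fills the gap.** Attachments C and G are described only as side-effect surveys. The post-study satisfaction surveys in section 10.0 are not defined separately. Since the index is the only survey that the protocol says assesses satisfaction, they are most likely the index again. They are also requested only after the study period, from participants who choose to continue, so they would leave out those who stopped.
6. **How far it reaches.** One of three objectives and one of two secondary endpoints. Section 6.0 gives a minimum of 30 and a target of 50 participants. Over the four-month period the index is due at baseline and four monthly visits, 1 + 4 = 5 times per participant. With full attendance that is 30 × 5 = 150 to 50 × 5 = 250 scores. All are quality-of-life scores, and none is a direct answer about the regimen.

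**The case against.** The case on the other side has four parts.

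- **The index is not uninformative.** It is validated, patient-reported and collected monthly alongside side-effect severity, so it says something about how patients experience the result. This stands. A reader might infer that the satisfaction objective cannot be answered, or that it has no valid measure at all. The documents do not support that. They support an indirect measure carrying the wrong label.
- **Giving the index before treatment is sound.** A reader might take the pre-drug administration as a defect in itself. It is not: in a single-arm study the baseline score is what makes change interpretable. The timing shows only that the baseline value is not satisfaction.
- **The attachments are not shown.** The list of side-effects in section 10.0 is introduced in a way that need not be exhaustive, and attachment G is a separate form from attachment C. A satisfaction question in attachment G therefore cannot be excluded. This also stands, so the claim is limited to what the protocol text describes.
- **The study is small and descriptive.** It is an open-label proof-of-concept study, the endpoint is secondary, and the instrument is disclosed openly. That limits the consequence but does not remove it. Where observations are simply reported, the label on the observation is the conclusion the reader takes away.

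It could also be said that rewording alone would remove the contradiction. It would, but the trial would then no longer address satisfaction with the regimen.

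**Conclusion.** The point holds as a mismatch between construct and label. The protocol sets out to evaluate satisfaction with weekly isotretinoin, names only a quality-of-life index for the purpose, and would report that index as satisfaction. It should be corrected, preferably before follow-up data are collected, because satisfaction not asked about during treatment cannot be reliably recovered afterwards.

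The size is one of three objectives and one of two secondary endpoints, for every participant. No bias or error rate can be attached to it. Efficacy, adverse effects and the enrolment target are unaffected.

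The conclusion rests on two assumptions: that attachment G holds only what section 10.0 describes, and that the undefined post-study surveys are the index. If attachment G already asks about satisfaction with the regimen, what remains is to name that item as the endpoint and relabel the index.

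**What to change.** 1. In sections 4.0, 8.0 and 10.0, call the index endpoint skin-related quality of life. Keep the baseline administration so that change can be reported.
2. Check attachment G. If it has no question on satisfaction with the regimen, add one (for example a five-point item) and add a matching field to the data sheet (attachment F). Ask it only after the drug has been started, and report it as the satisfaction endpoint.
3. Ask the same question at the last contact of participants who stop early, since they may be the least satisfied. It has to be obtained at that contact, because section 14.0 bars the investigator from the participant's records after withdrawal.
4. State in section 10.0 which form the post-study satisfaction surveys are.
5. If no question is added, reword the second objective and the endpoint in sections 2.0 and 4.0 so that they speak of quality of life only.

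The cost is wording in a few sections, one question on a survey patients already complete, and one column in the data sheet. The small downside is that a single added question is not a validated scale. Nothing in the change touches treatment.
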